5.2 Dosage

Based on randomization to receive the test article or the placebo, the patient will receive Comar Eye Dropper Bottles that contain pAF or control saline solution (NaCl 0.9% Baxter Medical). The patient will apply one drop 1-2 drops (one drop is approximately 50 μ L) in each eye four times daily for a total of 7 days. The patient will apply 1-2 drops (0.25mL) in each eye four times daily for a total of 7 days. Patients will be instructed to treat their eyes at regular intervals during the day, approximately at breakfast, lunch, dinner, bedtime, or the equivalent. Surgeons will administer the first dose of pAF or placebo to patients the morning of surgery, Day 1.

The study treatment assignment for each patient will be randomly selected. Neither the patient nor their doctors will know if they are receiving pAF or placebo. The eyedropper bottles containing pAF and the placebo will be packaged identically.

Patients will be instructed to use preservative free artificial tears from individual vials (any brand) no less than 3 but up to 8 times a day in both eyes during the first 7 days of the study.

5.3 Drug Dispensation and Randomization

Upon acceptance into the study, and prior to surgery, the patient will be randomized as to whether they will receive the pAF or the placebo. The study coordinator will notify CTRM who will then select, package and release Comar Eye Dropper Bottles containing pAF or the placebo saline solution (NaCl 0.9% Baxter Medical) to the clinical site. A small box of eight (8) eyedropper bottles containing 3.0 mL of either pAF or placebo will be provided in a Thermosafe box with dry ice to the patient for 7 days of treatment.

The small boxes will be packaged on dry ice and transported to the patient. The patient will be provided with the instructions on how to store the eye drops at home, how to use the eye drops and how to handle the dry ice. The patient will transport the eye drops to their home and immediately transfer them to their kitchen refrigerator freezer. For each day of use the patient will dispense the eye drops as follows:

1. The patient will remove the box containing the bottles from the freezer and remove a single bottle from the small box. They will verify that the lot number on the bottles match the labels on the small box. If the lot numbers on the bottle do not match the lot numbers on the small box, the patient will be instructed to notify the study coordinator. The study coordinator will notify CTRM, and CTRM will replace the bottle with the correct lot number. The patient will have to come to the Moran to trade out the bottle(s). **On Day 1 of surgery, surgeons will administer the first dose prior to patients leaving the surgery center).**
2. They will thaw the frozen fluid in the bottle by placing the bottle in their hand or by placing it at room temperature until the entire volume is completely thawed.

3. For the 1st daily application (e.g. morning), they will remove the cap from the bottle. They will invert the bottle over the right eye and squeeze to dispense 1-2 drops into the right eye. They will then invert the bottle over the left eye and squeeze to dispense 1-2 drops into the left eye. They will then tightly cap the bottle.
4. They will then place the thawed bottle into refrigerate at a temperature between 1°C and 10°C (e.g. refrigerator). They will not re-freeze the thawed bottle.
5. For each subsequent application of the day, they will remove the same thawed bottle that they used for the 1st application from the refrigerator and repeat steps 3 and 4.
6. After the final application of the day, they will place the bottle into a box provided to them for the placement of used bottles.
7. The patient will repeat these steps for each daily application.
8. After the 7th day of treatment, the patient will return all used and unused bottles to the clinic. This will allow us to account for drug dispensed and monitor compliance.
9. The patients will also voluntarily record if they missed any doses of their medication.

5.4 Assessment of Primary Endpoint(Safety)

Safety and tolerability will be evaluated by the PI from the findings of scheduled eye examinations at days 1 (day of surgery) through 8 (in-person follow-up visit) and at months 1, 3, 6 and 12 after initiation of pAF therapy. More frequent safety evaluations may be performed if clinically indicated or at the discretion of the investigator. Information from the eye examination at these additional safety evaluations will be collected and entered into the EDC as adverse events as appropriate.

All ocular adverse events will be recorded from randomization through Month 12. Any events that occur from time of consent to randomization will be recorded as medical history.

6 Safety Monitoring

6.1 Adverse Event Reporting

The site investigator is responsible for evaluating all adverse events at their Clinical Center and ensuring that they are properly reported. Only ocular adverse events (as specified in 6.1.2) that occur during this study will be recorded. The nature of each experience, date and time

(where appropriate) of onset, outcome, course, and relationship to treatment will be documented.

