5.1 Schedule of Events

| | Baseline | Day of Surgery (Friday) | | Days after Surgery | | | | | | | | | | |
|--|----------|----------------------------|---|--------------------|--------|--------|--------|--------|---------------------------------------|----------------------------|----------------------------|-----------------------------|------------------------------|---|
| | | Day 1 (AM) | Day 1 (2 nd visit post- surgery) | Day 3 | Day 4* | Day 5* | Day 6* | Day 7* | Day 8 Friday AM (in-person visit)* | Month 1 (Day 30±10)* | Month 3 (Day 90±14)* | Month 6 (Day 180±30)* | Month 12 (Day 365±30)* | |
| Informed Consent | X | | | | | | | | | | | | | |
| Eligibility | X | | | | | | | | | | | | | |
| Medical History | X | | | | | | | | | | | | | |
| Concomitant medications ² | X | X | X | X | X | X | X | X | X | X | X | X | X | |
| Randomization ³ | | | X | | | | | | | | | | | |
| PRK Surgery | | | X | | | | | | | | | | | |
| Dispense Masked Study Drug ⁴ | | | X | | | | | | | | | | | |
| Study Drug Compliance ⁵ | | | | X | X | X | X | X | | | | | | |
| Pain Assessment ⁶ | | | | X | X | X | X | X | | | | | | |
| Size of Epithelial Defect ⁷ | | | X | | X | X | X | X | X | | | | | |
| Uncorrected VA ⁸ | X | | | | | | | | | X | X | X | X | X |
| Manifest Refraction | X | | | | | | | | | | X | X | X | X |
| Target Post-OP Refraction | X | | | | | | | | | | | | | |
| BCVA ⁸ | X | | | | | | | | | | X | X | X | X |
| Ocular Surface Staining | X | | | | | | | | | | X | X | X | X |
| Corneal Topography | X | | | | | | | | | | X | X | X | X |
| Ocular Adverse Events | | | | X | X | X | X | X | X | | X | X | X | X |

1. The pre-op screening/baseline visit may be performed in 2 separate visits.

2. Record systemic medications at baseline and any subsequent changes; Record start and stop dates of ocular medications prescribed as standard care post-PRK surgery, note any deviations from prescribed regimens.

3. Randomization to study drug assignment will occur when patient presents day of surgery.

4. First dose of study drug applied to each eye at completion of surgery. Three additional doses administered by patient on day of surgery, then 4x per day through Day 7.

5. Patient will document each use of study drug and oral pain medication in diary.

6. Patient will assess highest level of daily pain/discomfort at the end of each day.

7. Grade defect dimensions until healed.

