6.1.1 Definition of Adverse Event and Serious Adverse Event

Adverse Event (AE) means any untoward medical occurrence associated with the use of an intervention in humans, whether or not considered intervention-related (21 CFR 312.32 (a)). An event constitutes a disease, a set of related signs or symptoms, or a single sign or symptom.

Serious Adverse Event (SAE): A serious adverse event (SAE) for this population is an adverse event that:

1. results in death; or
2. is life-threatening (the patient was, in the view of the site investigator, in immediate danger of death from the event as it occurred); or
3. requires inpatient hospitalization or prolongs an existing hospitalization; or
4. results in persistent or significant disability or incapacity; or
5. results in congenital anomaly/birth defect; or
6. any other event that, based upon appropriate medical judgment, may jeopardize the subject's health and may require medical or surgical intervention to prevent one of the other outcomes listed in this definition.

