6.1.5 Time Period for Adverse Events

For purposes of this study, events that occur following randomization through the last study visit will be reported as adverse events. Serious adverse events, unexpected medically attended events, and new onset chronic illnesses will be recorded from randomization through twelve months after the last study dose. Specifically, events that occur following consent to participate in the study, but prior to actual randomization, are not adverse events. These should be recorded as baseline conditions.

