12.6 Analysis of Safety Data

The primary safety analyses will be based on the as-treated population, defined as subjects who are randomized and receive at least one dose of study agent. Safety endpoints will include ocular adverse events, ophthalmic exam findings, and use of rescue treatments. The occurrence of ocular adverse events will be recorded from the time of randomization through the last study visit. AEs will be categorized by System Organ Class (SOC) Preferred Term (PT) using the Medical Dictionary for Regulatory Activities (MedDRA) and by severity using the Common Terminology Criteria for Adverse Events (CTCAE) dictionary.

In general, all AE tables will be presented by treatment group, causality and severity. Events in the right and left eyes will be considered as separate events. The following will be summarized and presented overall and by treatment group:

- The number and percentage of subjects experiencing an SAE.
- The number and percentage of subjects experiencing an SAE by preferred term and by severity of event.
- The number and percentage of subjects experiencing an SAE by preferred term and by relationship to study drug.

- The number and percentage of subjects experiencing an AE.
- The number and percentage of subjects experiencing an AE by preferred term and by severity of event.
- The number and percentage of subjects experiencing an AE by preferred term and by relationship to study drug.
- The number and percentage of AEs that cause a subject to discontinue study drug.
- The number and percentage of AEs leading to death.

13 Data Management

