11. SAFETY ANALYSES

11.1 Ocular Adverse Events

The primary safety analyses will be based on the as-treated population, defined as subjects who are randomized and receive at least one dose of study agent. Safety endpoints will include ocular adverse events, ophthalmic exam findings, and use of rescue treatments. The occurrence of ocular adverse events will be recorded from the time of randomization through the last study visit. AEs will be categorized by System Organ Class and Preferred Term using the Medical Dictionary for Regulatory Activities (MedDRA) and by severity using the Common Terminology Criteria for Adverse Events dictionary.

In general, all AE tables will be presented by treatment group, causality and severity. The following will be summarized and presented overall and by treatment group:

- The number and percentage of subjects experiencing an SAE
- The number and percentage of subjects experiencing an SAE by preferred term and by severity of event
- The number and percentage of subjects experiencing an SAE by preferred term and by relationship to study drug
- The number and percentage of subjects experiencing an AE
- The number and percentage of subjects experiencing an AE by preferred term and by severity of event
- The number and percentage of subjects experiencing an AE by preferred term and by relationship to study drug
- The number and percentage of AEs that cause a subject to discontinue study drug
- The number and percentage of AEs leading to death.

Adverse events will be coded using the Medical Dictionary for Regulatory Activities (MedDRA) central coding dictionary. Adverse events will be described in summary tables and in individual listings for the DSMB reports.

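### Protocol 6.1 limits adverse event recording to ocular events while 6.1.5 requires event classes with no ocular limit, and severity is graded on one scale but tabulated on another

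*Protocol*

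**What the plan says.** **Scope of recording.** Safety is the primary objective in both documents (Protocol section 2, SAP 3.1.1). Protocol 6.1 sets a restrictive rule: "Only ocular adverse events (as specified in 6.1.2) that occur during this study will be recorded". The matching row in the Protocol 5.1 schedule is labelled "Ocular Adverse Events", and Protocol 12.6 says "The occurrence of ocular adverse events will be recorded from the time of randomization through the last study visit".

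Protocol 6.1.5 sets a wider rule: "Serious adverse events, unexpected medically attended events, and new onset chronic illnesses will be recorded from randomization through twelve months after the last study dose". It does not mention the eye. The SAE definition in 6.1.1 is not ocular either. It covers death, for example, and any event that "requires inpatient hospitalization or prolongs an existing hospitalization".

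**Severity.** Protocol 6.1.2 has the site investigator record severity as mild, moderate or severe, using definitions written into the protocol. Protocol 12.6 categorises AEs "by severity using the Common Terminology Criteria for Adverse Events (CTCAE) dictionary", and SAP 11.1 does the same, "by severity using the Common Terminology Criteria for Adverse Events dictionary". Both documents make severity a general feature of the output. In the protocol's words: "In general, all AE tables will be presented by treatment group, causality and severity".

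**The concern.** An investigator whose patient is hospitalised for a non-ocular reason is told by 6.1 not to record the event and by 6.1.5 to record it. No section says which rule governs. The content of the safety dataset would then depend on which section the site followed, in a trial whose first purpose is to describe safety. A zero in an SAE or death table could not be interpreted until the reader knew whether non-ocular events were eligible to appear in it.

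The severity mismatch is a separate, smaller fault. The tables call for a classification that the investigator is not asked to make.

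**Working it through.** No stated figure is in dispute and the power calculation is unaffected. The check sets the rules side by side, counts the tables they reach, and compares two time windows.

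**1. Two test events**

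| Place | Non-ocular hospitalisation | Non-ocular, non-serious new chronic illness |
|---|---|---|
| Protocol 6.1 | Not recorded | Not recorded |
| Protocol 5.1 schedule row | No place for it | No place for it |
| Protocol 12.6, recording sentence | Refers to ocular events only | Refers to ocular events only |
| Protocol 6.1.1 | Meets the SAE definition | Not an SAE |
| Protocol 6.1.5 | Recorded | Recorded |
| Protocol 6.1.8 | Reported to the Data Coordinating Center within 24 hours | Not covered |
| SAP 3.2.4, survival tracking | Covers it only if fatal | Not covered |

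Protocol 6.1.6 speaks of all adverse events, but as a subsection of 6.1 it could inherit the ocular limit. It is not counted on either side. The contradiction rests on 6.1 against 6.1.5.

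**2. Could 6.1.5 mean only ocular members of its classes?** Where the authors wanted serious events confined to the eye, they said so: the study discontinuation rule in Protocol section 11 is worded for ocular serious events. Section 6.1.5 has no such word, and its medically attended and chronic-illness classes read poorly as eye-only categories.

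**3. Tables reached.** Protocol 12.6 and SAP 11.1 list the same summaries: 3 on SAEs + 3 on AEs + 1 on discontinuation of study drug + 1 on death = 8.
- Section 6.1.1 defines an SAE as a kind of AE. An omitted non-ocular SAE is therefore missing from the AE summaries as well as the SAE summaries.
- If the event stops study drug or is fatal, it is also missing from the discontinuation or death summary.
- Omitted non-serious events from the 6.1.5 classes affect the AE summaries and, if they stop study drug, the discontinuation summary.

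So all 8 can be affected. The chi-squared and mid-p comparison of AE rates in SAP 11.1 uses the same record.

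**4. Severity.** Levels recorded under 6.1.2: 3. Levels with a stated CTCAE counterpart: 0. The only central coding step described in 6.1.6 is MedDRA, and no re-grading step appears. Two of the 8 summaries name severity explicitly, but the general sentence quoted above extends it to AE tables as a whole.

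**5. Recording window.** Study drug runs through Day 7 (Protocol 5.1, footnote 4). Taking twelve months as 365 days, the 6.1.5 window closes at 7 + 365 = Day 372. The Month 12 visit is Day 365 ± 30, that is, Day 335 to Day 395. The window can therefore stay open for up to 372 − 335 = 37 days after an early final visit. This matters for the cost of the fix.

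**The case against.** The strongest reply is that the plan has two tiers. Routine AE recording is ocular, as 5.1, 5.4, 6.1, 12.6, the SAP 3.2.4 endpoint list and the SAP 11.1 heading indicate, while SAEs travel through the separate process in 6.1.8. On that reading the fault is little more than the word *only* in 6.1.

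Much of this stands for SAEs. A reader might infer that non-ocular SAEs and deaths would go uncollected altogether. The documents do not support that: 6.1.8 requires SAE reports within 24 hours with no ocular limit, the medical monitor signs off each one, the reports are retained, and SAP 3.2.4 tracks survival. For SAEs the main risk is omission from the AE record and tables. The two-tier reading still does not settle the matter, because no section states it, none says the 6.1.8 reports feed the tables, and it leaves the non-serious 6.1.5 classes unexplained.

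A reader might also take the cross-reference in 6.1 to 6.1.2 as closing the list of recordable ocular events. Section 5.4 says all ocular AEs are recorded, so this is a wording risk and not a second contradiction.

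On severity, SAP 8.6 defers derived variables to dataset specifications, where a mapping could be placed. It does not promise one.

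**Conclusion.** The point holds as a contradiction between stated rules. Protocol 6.1 and 6.1.5 cannot both be followed for a non-ocular SAE, or for a non-ocular event in either of the other 6.1.5 classes, and the conflict can reach all 8 planned summaries and the between-arm AE comparison. The severity mismatch also holds: three recorded levels, none with a stated CTCAE equivalent.

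Confidence is high on the text and lower on the practical consequence, which depends on how the site and the Data Coordinating Center would handle the 6.1.8 reports. The documents give no AE rate, so the number of events that might be omitted cannot be estimated. A reader might want to attach an upper confidence limit to a zero count, but no planned analysis uses one and the conflict does not depend on it. This should be fixed; it does not undermine the collection of ocular AEs, which 5.4 secures.

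**What to change.** - **Scope.** Amend the restrictive sentence in Protocol 6.1 so that it covers all ocular AEs, as 5.4 does, plus the classes 6.1.5 already requires. Make the 5.1 schedule row, 6.1.6 and the recording sentence in 12.6 match.
- **Tables.** State in Protocol 12.6 and SAP 11.1 whether the SAE, AE and death tables include non-ocular events, so that a zero can be interpreted.
- **Event list in 6.1.2.** Say that it is not exhaustive. Do not label its events anticipated or expected: expectedness feeds the unanticipated-problem rule (6.1.7), the follow-up duty (6.1.9) and the study discontinuation rule (section 11), and such a label could take events out of them.
- **Severity.** Use one scale in 6.1.2, 12.6 and SAP 11.1, or state a mapping between the two.

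The cost is wording in both documents, a schedule row label, a form field and slightly more data entry. It is not wholly confined to scheduled visits: a participant whose Month 12 visit falls as early as Day 335 may need a brief later contact, because the 6.1.5 window closes near Day 372.

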6.1.1 Definition of Adverse Event and Serious Adverse Event

Adverse Event (AE) means any untoward medical occurrence associated with the use of an intervention in humans, whether or not considered intervention-related (21 CFR 312.32 (a)). An event constitutes a disease, a set of related signs or symptoms, or a single sign or symptom.

Serious Adverse Event (SAE): A serious adverse event (SAE) for this population is an adverse event that:

1. results in death; or
2. is life-threatening (the patient was, in the view of the site investigator, in immediate danger of death from the event as it occurred); or
3. requires inpatient hospitalization or prolongs an existing hospitalization; or
4. results in persistent or significant disability or incapacity; or
5. results in congenital anomaly/birth defect; or
6. any other event that, based upon appropriate medical judgment, may jeopardize the subject's health and may require medical or surgical intervention to prevent one of the other outcomes listed in this definition.

6.1.2 Classification of an Adverse Event (Relatedness, Severity, and Expectedness)

Relatedness: The suspected relationship between study interventions and any adverse event will be determined by the site investigator using the criteria below. Relatedness must be assessed by an investigator and may not be assessed by a research coordinator.

- Not Related: The event is clearly related to other factors, such as the subject's clinical state, therapeutic interventions, or concomitant drugs administered to the subject.
- Possibly Related: The event follows compatible temporal sequence from the time of beginning the assigned study intervention, but could have been produced by other factors such as the subject's clinical state, therapeutic interventions, or concomitant drugs administered to the subject.

- Probably Related: The event follows a reasonable temporal sequence from the time of beginning the assigned study intervention, and cannot be reasonably explained by other factors such as the subject's clinical state, therapeutic interventions, or concomitant drugs administered to the subject.

Severity:

The severity, which is a measure of intensity, of clinical adverse events and laboratory abnormalities will be recorded by the site investigator and categorized. The following guidelines will be used to describe severity.

- Mild: The event requires minimal or no treatment and does not interfere with the participants daily activities.
- Moderate: The event results in a low level of inconvenience or concern with the therapeutic measures. Moderate events may cause some interference with functioning.
- Severe: The event interrupts a participants usual daily activity and may require systemic drug therapy or other treatment. Severe events are usually potentially life-threatening or incapacitating. Of note, the term "severe" does not necessarily equate to "serious".

Expectedness of the Event:

All adverse events, including serious adverse events, will be evaluated as to whether their occurrence was expected or unexpected. An AE will be considered unexpected if the nature, severity, or frequency of the event is not consistent with the risk information described for the study intervention. The following events will be reported as AEs::

- Infection
- Delayed healing of the epithelial defect (after the 7-day post-surgery visit)
- Scarring or haze
- Severe irritation of conjunctiva or periocular skin in the first week
- Poor refractive outcome (worse than 20/40 at 3 months or beyond)
- Pain or severe irritation at 3 months or beyond
- Corneal erosion
- Corneal haze
- Need for touch up surgery

There is a theoretical risk of infection with amniotic fluid drops. A patient could have an immune reaction to the study drops.

6.1.3 Treatment or Action Taken:

For each adverse event, the site investigator will record whether an intervention was required:

- Medical or surgical procedure
- Concomitant medication: started, changed, or discontinued
- Other, specify
- No action taken

6.1.4 Outcome of Event:

Finally, the site investigator will record the clinical outcome of each adverse event as follows:

- Death
- Recovered and the patient returned to baseline status
- Recovered with permanent sequelae
- Symptoms persist

